3.1.1 Special notes on the assessment of target lesions

3.1.1.1 Lymph nodes

Lymph nodes merit special mention since they are normal anatomical structures which may be visible by imaging even if not involved by tumor. Pathological nodes which are defined as measurable and may be identified as target lesions must meet the criterion of a **short axis of ≥ 15 mm by CT scan**. Only the *short* axis of these nodes will contribute to the baseline sum. Nodes that have a short axis <10 mm are considered non-pathological and should not be recorded or followed.

3.1.1.2 Target lesions that become ‘too small to measure’

All lesions (nodal and non-nodal) recorded at baseline should have their actual measurements recorded at each subsequent evaluation, even when very small (e.g. 2 mm). If the radiologist is able to provide an actual measurement, that should be recorded, even if it is below 5 mm.

However, when such a lesion becomes difficult to assign an exact measure to then:

- if it is the opinion of the radiologist that the lesion has likely disappeared, the measurement should be recorded as 0 mm.
- if the lesion is believed to be present and is faintly seen but too small to measure, a default value of 5 mm should be assigned (*note*: in case of a lymph node believed to be present and

faintly seen but too small to measure, a default value of 5 mm should be assigned in this circumstance as well). This default value is derived from the 5 mm CT slice thickness (but should not be changed with varying CT slice thickness).

3.1.1.3 Target lesions that split or coalesce on treatment

- When non-nodal lesions ‘fragment’, the longest diameters of the fragmented portions should be added together to calculate the target lesion sum.
- As lesions coalesce, a plane between them may be maintained that would aid in obtaining maximal diameter measurements of each individual lesion. If the lesions have truly coalesced such that they are no longer separable, the vector of the longest diameter in this instance should be the maximal longest diameter for the ‘coalesced lesion’

3.2 Evaluation of non-target lesions

While some non-target lesions may actually be measurable, they need not be measured and instead should be assessed only qualitatively at the time points specified in the protocol.

Complete Response (CR): Disappearance of all non-target lesions. All lymph nodes must be non-pathological in size (< 10 mm short axis).

Non-CR/Non-PD: Persistence of one or more non-target lesion(s).

Progressive Disease (PD): *Unequivocal progression* of existing non-target lesions. (*Note*: the appearance of one or more new lesions is also considered progression).

3.2.1 Special notes on assessment of non-target lesions

The concept of progression of non-target disease requires additional explanation as follows:

3.2.1.1 When the subject also has measurable disease

- To achieve ‘unequivocal progression’ on the basis of the non-target disease, there must be an overall level of substantial worsening in non-target disease such that, even in presence of SD or PR in target disease, the overall tumor burden has increased sufficiently to merit discontinuation of therapy.
- A modest ‘increase’ in the size of one or more non-target lesions is usually not sufficient to qualify for unequivocal progression status.

3.2.1.2 When the subject has only non-measurable disease

- To achieve ‘unequivocal progression’ on the basis of the non-target disease, there must be an overall level of substantial worsening such that the overall tumor burden has increased sufficiently to merit discontinuation of therapy.
- A modest ‘increase’ in the size of one or more non-target lesions is usually not sufficient to qualify for unequivocal progression status.
- Because worsening in non-target disease cannot be easily quantified (by definition: if all lesions are non-measurable) a useful test that can be applied when assessing subjects for unequivocal progression is to consider if the increase in overall disease burden based on the change in non-measurable disease is comparable in magnitude to the increase that would be required to declare PD for measurable disease: i.e. an increase in tumor burden representing an additional 73% increase in ‘volume’ (which is equivalent to a 20% increase diameter in a

measurable lesion). Examples include an increase in a pleural effusion from ‘trace’ to ‘large’, an increase in lymphangitic disease from localized to widespread, or may be described in protocols as ‘sufficient to require a change in therapy’.

- If ‘unequivocal progression’ is seen, the subject should be considered to have had overall PD at that point.

3.2.1.3 Tumor markers

Tumor markers will not be used to assess objective tumor responses.

3.3 New lesions

The appearance of new malignant lesions denotes disease progression. The finding of a new lesion should be unequivocal: i.e. not attributable to differences in scanning technique, change in imaging modality or findings thought to represent something other than tumor (for example, some ‘new’ bone lesions may be simply healing or flare of pre-existing lesions). This is particularly important when the subject’s baseline lesions show partial or complete response. For example, necrosis of a liver lesion may be reported on a CT scan report as a ‘new’ cystic lesion, which it is not.

A lesion identified on a follow-up study in an anatomical location that was *not* scanned at baseline is considered a new lesion and will indicate disease progression. An example of this is the subject who has visceral disease at baseline and while on study has a CT or MRI brain scan ordered which reveals metastases. The subject’s brain metastases are considered to be evidence of PD even if he/she did not have brain imaging at baseline.

If a new lesion is equivocal, for example because of its small size, continued therapy and follow-up evaluation will clarify if it represents truly new disease. *If repeat scans confirm there is definitely a new lesion, then progression should be declared using the date of the initial scan.*

4 RESPONSE CRITERIA

4.1 Time point response

A response assessment should occur at each time point specified in the protocol.

For subjects who have **measurable disease** at baseline [Table 1](#) provides a summary of the overall response status calculation at each time point.

Table 1. Time point response: subjects with target (+/- non-target) disease.			
Target lesions	Non-target lesions	New lesions	Overall response
CR	CR	No	CR
CR	Non-CR/non-PD	No	PR
CR	Not evaluated	No	PR

Table 1. Time point response: subjects with target (+/- non-target) disease.

Target lesions	Non-target lesions	New lesions	Overall response
PR	Non-PD or not all evaluated	No	PR
SD	Non-PD or not all evaluated	No	SD
Not all evaluated	Non-PD	No	NE
PD	Any	Yes or No	PD
Any	PD	Yes or No	PD
Any	Any	Yes	PD

CR = complete response, PR = partial response, SD = stable disease, PD = progressive disease, NE =not evaluable.

4.1.1 Missing assessments and not evaluable designation

When no imaging/measurement is done at all at a particular time point, the subject is **not evaluable (NE)** at that time point. If only a subset of lesion measurements are made at an assessment, the case is also considered NE at that time point, unless a convincing argument can be made that the contribution of the individual missing lesion(s) would not have changed the assigned time point response.

4.1.2 Confirmation Scans

- **Verification of Response:** Confirmation of PR and CR is required within 4 weeks to ensure responses identified are not the result of measurement error.

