Safety lead-in: There will be continuous monitoring of safety. Initially approximately 10 subjects will be enrolled and followed for at least 4 weeks of safety assessment from the start of study drug administration before additional subjects are enrolled in the study to ensure there is no major safety signal with the combination. Any findings will be discussed between the BMS Medical Monitor and investigators and an agreement will be reached as to whether a lower dose or an alternate dose schedule should be examined or whether any additional treatment guidelines should be implemented prior to enrollment of additional subjects on study.

[figure not shown]
Following each treatment cycle (12 weeks of study therapy consisting of 6 doses of nivolumab given Q2W, 2 doses of ipilimumab given Q6W, and 3 doses of lirilumab given Q4W), the decision to treat a subject with additional study therapy will be based on tumor assessment done Q8W (evaluation performed Q8W and completed before study therapy is continued). Treatment decisions related to subject management will be based on investigator-assessed radiographic assessment using RECIST v1.1 (see [Appendix 3](#)). Subjects with an overall response of SD, PR, or CR-unconfirmed at the time of each assessment may continue study drug. Subjects will generally be allowed to continue study drug until the first occurrence of any of the following: 1) achievement of CR-confirmed; 2) PD (confirmed or unconfirmed); 3) clinical deterioration suggesting that no further benefit from treatment is likely; 4) intolerability to therapy; 5) meeting criteria for discontinuation of study therapy as outlined in [Sections 3.5](#) and [4.9.5](#) or 6) maximum treatment duration of 8 treatment cycles. (See [section 3.5.1](#)).

The subjects listed above will enter the clinical follow-up period, with visits scheduled on Days 30, 60, 100, and 150 to monitor for AEs.

A study period schematic is presented below in [Figure 3.1.5-1](#) and [Figure 3.1.5-2](#).

[figure not shown]
For the purposes of subject management, clinical decision-making will be based on RECIST v1.1. Therefore, timepoint tumor response evaluations will be recorded on the CRF based on investigators' assessments using RECIST v1.1 criteria.

Figure 3.1.5-1: Study Schematic for the Signal Detection in SCCHN with Lirilumab, Nivolumab, and Ipilimumab Combination (Part 5)

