BOR is the best response designation recorded from the start of the study treatment until the end of treatment taking into account any requirement for confirmation, based on RECIST v1.1 criteria. CR or PR determinations included in the BOR assessment must be confirmed by a consecutive second (confirmatory) evaluation meeting the criteria for response that is performed at least 4 weeks after the criteria for response are first met. The above will be determined based on tumor measurements occurring Q8W (\pm 7days) during the treatment period (or Q6W (\pm 7days) for 1 year [48 weeks] and Q12W (\pm 7days) afterwards for the Signal Detection in SCCHN with Lirilumab, Nivolumab, and Ipilimumab Combination [Part 5] and once during the clinical follow-up period.

Other efficacy endpoints include the following:

OS is defined as the time from randomization to the date of death. A subject who has not died will be censored at last known date alive. OS will be followed continuously while subjects are on the study drug and every 3 months for up to 3 years following the first dose of study drug via in-person or phone contact after subjects discontinue the study drug.

PFS is defined as the time from randomization to the date of the first documented tumor progression (per RECIST v1.1). Subjects who die without a reported prior progression will be considered to have progressed on the date of their death. Subjects who did not progress or die will be censored on the date of their last evaluable tumor assessment. Subjects who did not have any on-study tumor assessments and did not die will be censored on the date they were randomized. Subjects who started any subsequent anti-cancer therapy without a prior reported progression will be censored at the last evaluable tumor assessment prior to initiation of the subsequent anti-cancer therapy.

DOR is defined as the time between the date of first confirmed response to the date of the first documented tumor progression (per RECIST 1.1), or death due to any cause, whichever occurs first. Subjects who neither progress nor die will be censored on the date of their last evaluable tumor assessment. Subjects who started any subsequent anti-cancer therapy without a prior reported progression will be censored at the last evaluable tumor assessment prior to or on initiation of the subsequent anti-cancer therapy. DOR will be evaluated for responders (confirmed CR or PR) only.

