4.2 Best Overall Response: all time points

The *best overall response* is determined once all the data for the subject is known. It is the best response recorded from the start of the study treatment until the end of treatment taking into account any requirement for confirmation. The subject’s best overall response assignment will depend on the findings of both target and non-target disease and will also take into consideration the appearance of new lesions.

Best response is defined as the best response across all time points with subsequent confirmation. Complete or partial responses may be claimed only if the criteria for each are met at a subsequent time point as specified in the protocol (generally 4 weeks later).

In this circumstance, the best overall response can be interpreted as specified in [Table 2](#). When SD is believed to be best response, it must meet the protocol specified minimum time from baseline.

Measurements must have met the SD criteria at least once after study entry at a minimum interval (in general not less than 6–8 weeks) that is defined in the study protocol.

Table 2. Best overall response when confirmation of CR and PR IS required.

Overall response	Overall response	BEST overall response
First time point	Subsequent time point	
CR	CR	CR
CR	PR	SD, PD or PR ^a
CR	SD	SD provided minimum criteria for SD duration met, otherwise, PD
CR	PD	SD provided minimum criteria for SD duration met, otherwise, PD
CR	NE	SD provided minimum criteria for SD duration met, otherwise NE
PR	CR	PR
PR	PR	PR
PR	SD	SD
PR	PD	SD provided minimum criteria for SD duration met, otherwise, PD
PR	NE	SD provided minimum criteria for SD duration met, otherwise NE
NE	NE	NE

CR = complete response, PR = partial response, SD = stable disease, PD = progressive disease, NE = not evaluable.

a If a CR is truly met at first time point, then any disease seen at a subsequent time point, even disease meeting PR criteria relative to baseline, makes the disease PD at that point (since disease must have reappeared after CR). Best response would depend on whether minimum duration for SD was met. However, sometimes ‘CR’ may be claimed when subsequent scans suggest small lesions were likely still present and in fact the subject had PR, not CR at the first time point. Under these circumstances, the original CR should be changed to PR and the best response is PR.

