4.2.1.1 Objective Response Rate (ORR)

ORR is defined as the total number of participants whose best overall response (BOR) is either a complete response (CR) or partial response (PR) divided by the total number of participants in the population of interest. BOR for a participant will be **derived** using investigator-provided tumor measurements per RECIST v1.1 for all Parts. BOR for a participant will also be assessed by the investigator per RECIST v1.1 for Parts 3 and Part 5. All summaries or listings of BOR will be using derived BOR per RECIST v1.1 for all Parts.

BOR for a participant is defined as the best response designation recorded between the date of first dose (or date of randomization) and the date of first objectively documented progression per RECIST v1.1 or the date of subsequent therapy, whichever occurs first. CR or PR determinations included in the BOR assessment must be confirmed by a second scan no less than 4 weeks after the criteria for response are first met. For participants without documented progression or subsequent therapy, all available response designations will contribute to the BOR assessment. For participants who continue treatment beyond progression or begin subsequent therapy, the BOR should be determined based on response designations recorded up to the time of the initial RECIST v1.1 defined progression or subsequent therapy, whichever occurs first.

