subsequent anti-cancer therapy, all available response designations will contribute to the BOR determination. For subjects who continue treatment beyond progression, the BOR should be determined based on response designations recorded up to the time of the initial RECIST 1.1-defined progression. Additionally, the following will be applicable for BOR evaluation:

- For a BOR of complete response (CR) or partial response (PR), the response assessment must have been confirmed by a consecutive assessment no less than 4 weeks (28 days) later.
- For a BOR of stable disease (SD), the minimum criteria for SD duration (e.g, 6-8 weeks) must have been satisfied (42 days will be used to derive SD). This time minimum criteria only applies to derived BOR of SD, not to per timepoint evaluation.

Duration of response (DOR) for a subject with confirmed response is defined as the time from first response (CR or PR) to the date of the first documented tumor progression as determined using RECIST 1.1 criteria or death due to any cause, whichever occurs first. Subjects who remain alive and have not progressed will be censored on the date of their last tumor assessment (prior to subsequent cancer therapy). Response duration will only be evaluated in subjects with objective response of CR or PR.

Time to response (TTR) for a subject is defined as the time from date of first dose of study medication to the date of the first documented objective response (CR or PR). Time to response will only be evaluated in subjects with objective response of CR or PR.

Progression-free survival (PFS) for a subject is defined as the time from the date of first dose of study medication to the date of first documented disease progression or death due to any cause, if death occurred within 100 days after last lirilumab or nivolumab dose of study drug. Clinical deterioration in the absence of radiographic evidence is not considered progression for the purpose of determining PFS. Subjects who remain alive and have not progressed will be censored on the last tumor assessment date (prior to subsequent cancer therapy). Subjects who did not have any on study tumor assessment and did not die will be censored on the date of first dose of study medication.

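### Protocol Appendix 3 sets 4 weeks as the maximum time to confirm a response, but Protocol 8.3 and the SAP set it as the minimum; 8-weekly scans cannot meet the maximum

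*Protocol*

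**What the plan says.** Five passages give a confirmation rule for CR and PR under RECIST v1.1.

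- Protocol Appendix 3, section 4.1.2: "Confirmation of PR and CR is required within 4 weeks to ensure responses identified are not the result of measurement error".
- Protocol Appendix 3, section 4.2: "Complete or partial responses may be claimed only if the criteria for each are met at a subsequent time point as specified in the protocol". A parenthesis adds that this is usually about 4 weeks on.
- Protocol 8.3, in the BOR definition: a consecutive second evaluation "that is performed at least 4 weeks after the criteria for response are first met".
- SAP 4.2.1.1: a CR or PR "must be confirmed by a second scan no less than 4 weeks after the criteria for response are first met".
- SAP general efficacy definitions, placed after 4.2.1.4: "the response assessment must have been confirmed by a consecutive assessment no less than 4 weeks (28 days) later".

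The irRECIST appendix (Appendix 2, section 4.1.1), which investigators use in Parts 1 and 2, also sets 4 weeks as a minimum for irPR.

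Appendix 3 is in active use. Protocol 5.4 cites it for deriving tumor responses and for the specifics of RECIST v1.1 in Parts 3 and 5. Protocol 3.1.3 and 3.1.5 cite it for treatment decisions in those parts. In Part 5 the confirmed or unconfirmed status of a CR matters for treatment: "Subjects with an overall response of SD, PR, or CR-unconfirmed at the time of each assessment may continue study drug" (Protocol 3.1.5), and Protocol 3.5 lists confirmed CR, with a pointer to Appendix 3, among the reasons to discontinue.

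On reporting, SAP 4.2.1.1 states "All summaries or listings of BOR will be using derived BOR per RECIST v1.1 for all Parts". SAP 4.1, however, says that investigator-assessed BOR for Parts 3 and 5 will be listed, and Protocol 8.3.2.2 makes investigator-assessed ORR a Part 3 secondary endpoint. SAP 7.1 restricts all Part 3 and Part 5 results to listings.

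**The concern.** Confirmation decides whether a CR or PR counts toward BOR and ORR. One operative section gives that rule with the inequality reversed. An investigator in Part 3 or 5 who opens Appendix 3 at the section on confirmation scans finds an upper limit that the trial's scan schedule cannot meet. Neither document says which rule the investigator-assessed BOR follows. If some investigators apply section 4.1.2 literally and others apply Protocol 8.3, the same scan sequence can be recorded as confirmed at one site and unconfirmed at another. It can also differ between the investigator's call and the derived one.

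**Working it through.** The plan states no figure to reproduce here. The check compares the rules with each other and then with the scan calendar.

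**1. The rules side by side** (t = days from first meeting response criteria to the confirming scan)

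| Source | Rule |
|---|---|
| Protocol Appendix 3, 4.1.2 | t ≤ 28 |
| Protocol Appendix 3, 4.2 | as the protocol specifies |
| Protocol 8.3 | t ≥ 28 |
| SAP 4.2.1.1 | t ≥ 28 |
| SAP general definitions | t ≥ 28 |

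The first rule and the minimum share one value, t = 28. Section 4.1.2 is the only passage that sets a maximum.

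**2. The calendar.** Protocol 8.3.1.2 (Part 3) and 8.3.2.4 (Part 5) schedule scans every 8 weeks, ± 7 days, to Week 48, then every 12 weeks, ± 7 days. Each scan can move 7 days either way, so consecutive scans D days apart nominally have an actual gap of D − 14 to D + 14.

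- Every 8 weeks: 56 − 14 = 42 to 56 + 14 = 70 days.
- Every 12 weeks: 84 − 14 = 70 to 84 + 14 = 98 days.

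Every scheduled pair satisfies t ≥ 28 and none satisfies t ≤ 28. I found no separate confirmation scan in the schedules. Protocol 5.4 allows extra assessments when the investigator is concerned about progression, which is a different purpose.

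**3. A second conflict that touches this one.** The BOR paragraph of Protocol 8.3 gives a 6-weekly schedule for Part 5, against 8-weekly in Protocol 8.3.2.4 and Table 5.1.4-2. At 6 weeks the gap is 42 − 14 = 28 to 42 + 14 = 56 days, so only the shortest possible gap would meet section 4.1.2.

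**4. Illustration of size under a literal reading.** Protocol 8.1.4 uses 50 responders among 150 Arm A subjects. Let f be the share of responders confirmed only at the next scheduled scan. The documents do not give f, so it is an assumption. Then confirmed ORR under section 4.1.2 = 50 × (1 − f) / 150.

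- f = 0: 50/150 = 33.3%.
- f = 0.5: 25/150 = 16.7%.
- f = 1: 0/150 = 0%.

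Under the minimum of 28 days, confirmation at the next scheduled scan counts, so the figure stays at 33.3% for the values of f shown.

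**The case against.** The strongest reply is that this is one careless sentence with little reach, and much of that stands.

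- The derived BOR rule is stated twice in the SAP, clearly and with the 28 days spelled out. A programmer who follows it will not use section 4.1.2.
- Protocol 8.3 defines BOR in general terms and is not limited to the derived version. Section 4.2 of Appendix 3, which is where BOR is defined, hands the timing back to the protocol. An investigator reading the whole document could reach the correct rule.
- In Parts 1 and 2, the only parts with summary tables, investigators use irRECIST with its own 4-week minimum.
- Parts 3 and 5 appear in listings only, so the SAP plans no summary of investigator-assessed ORR.

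A reader might infer that investigator-assessed ORR and derived ORR are built on opposite rules by design. The documents do not support that. No passage assigns section 4.1.2 to one and the minimum to the other, and Appendix 3 is cited for derived responses as well as for investigators' decisions. A reader might also take 0% as the expected confirmed ORR under Appendix 3. It is only the bound at f = 1 under a literal reading.

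The reply does not remove the contradiction. Section 4.1.2 still gives a rule that the schedule cannot satisfy, in the appendix to which Part 3 and Part 5 investigators are sent, and nothing says which rule their BOR follows.

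**Conclusion.** The concern holds in a limited form. Appendix 3, section 4.1.2, is wrong as written: it conflicts with section 4.2 of the same appendix, with Protocol 8.3 and with the SAP, and scheduled scans 42 to 70 (later 70 to 98) days apart cannot meet it.

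The exposure is investigator-assessed BOR and ORR in Parts 3 and 5. There, literal use of section 4.1.2 would leave unconfirmed every response whose second reading came at a scheduled scan. How many responses that would affect cannot be known from the documents. Derived BOR and ORR are unaffected provided the SAP definitions are followed, and the problem does not extend to investigator assessments in Parts 1 and 2. The conclusion assumes the 8-weekly schedule for Part 5; under the conflicting 6-weekly statement a scheduled pair could meet both rules, but only at exactly 28 days.

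**What to change.** For endpoint determination, reword Appendix 3, section 4.1.2, so that a CR or PR is confirmed by a second scan no less than 4 weeks (28 days) after the criteria are first met, as in Protocol 8.3 and SAP 4.2.1. Add a sentence to the protocol and SAP that the same rule applies to investigator-assessed BOR in Parts 3 and 5. At the same time, resolve whether that BOR is listed at all, since SAP 4.1 and 4.2.1.1 disagree, and correct the Part 5 scan interval so that Protocol 8.3 gives one value.

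Separately, the Part 5 passages on continuing or stopping treatment by confirmed or unconfirmed CR (Protocol 3.1.5 and 3.5) refer to Appendix 3 and must be reconciled with it by those responsible for clinical management. This point does not propose what that clinical rule should be.

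The cost is a few sentences of text. The endpoint change needs no new scans and leaves the derived analysis as the SAP already defines it.
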